8.5 Study Termination

NCI, DCP, as the study sponsor, has the right to discontinue the study at any time.

9. CORRELATIVE/SPECIAL STUDIES

9.1 Rationale for Methodology Selection

Our primary outcome is to compare changes in gastric mucosal IL-1 β cytokine levels (as quantified with Luminex assay technology) after a 6-month intervention period in participants randomly assigned to receive Meriva® vs placebo. Secondary laboratory and biomarker outcomes include the assessment of additional gastric mucosal cytokine/chemokine levels (IL-8, TNF α , and IP-10, quantified with Luminex assay), gastric mucosal DNA damage (assessed by flow cytometry), and correlations with proinflammatory cytokine genotypes. The choice of these endpoints is based upon emerging preliminary data and the Vanderbilt University group's extensive experience in the field, as described in further detail in the following sections.

Gastric mucosal cytokines (Luminex assay). We will focus on IL-1β as a primary endpoint for this phase 2 trial, based on its compelling implication in H. pylori-associated gastric cancer risk, ⁵⁵⁻⁵⁹ and novel data generated by our investigative team showing that Meriva® administration can lead to decreased IL-1β protein levels in murine gastric samples (See Figure 1, Section 2.3). In Figure 1D, a significant decrease in mucosal IL-1β levels in mouse models is noted, as measured by Luminex assay. Intriguingly, in ongoing studies with human gastric biopsy samples obtained from patients with H. pylori-associated gastritis and gastric cancer, the Wilson lab at Vanderbilt has observed an increase in IL-1β in gastric tumors compared to paired non-tumor specimens, using Luminex assay technology. In addition, IL-8, TNF- α , and IP-10 (CXCL10) were increased in

MAY2015-05-01 Version 4.0, Amendment 6 May 13, 2019

both *H. pylori* infection and gastric cancers, as compared to histologically normal control tissues. Examination of IL-8, TNF- α , and IP-10 (CXCL10) mucosal levels have therefore been included in the present trial as secondary biomarker outcomes.

We will use the 38-plex Luminex assay kit (HCYTOMAG-60K MILLIPLEX MAP Human Cytokine/Chemokine Magnetic Bead Panel). Importantly, the Department of Pathology and Laboratory Medicine at the University of Puerto Rico has extensive expertise in multi-analyte, Luminex-based cytokine profiling in gastrointestinal tissues, including studies evaluating *H. pylori*-induced gastric inflammation and ulcerative colitis. 60, 61

The scoring methods for Histology Gastric Score will follow the established protocol previously applied and reported by Correa and colleagues. ⁶²

Proinflammatory cytokine genotypes (IL-1 β , IL-8, and TNF α SNPs) may correlate with gastric adenocarcinoma risk in the setting of active or prior *H. pylori* infection. ⁶³ In our population-based studies in Honduras, we have begun to characterize these risk genotypes in the general population. ^{59, 64} Whole blood DNA will be obtained at the baseline visit for the determination of the risk genotype status and to fully characterize the host, which is part of our standard protocol in Central America. These genotypes, or other future genotypes, may provide the opportunity for precision medicine in the future and will be included as secondary outcome analyses, for the purpose of augmenting limited existing data and generating new hypotheses worthy of application to future gastric cancer chemoprevention studies in this population.

9.2 Comparable Methods

All methodology is identical to that used in previous, published research.^{61,48}

All samples will be shipped in compliance with the International Air Transport Association (IATA) Dangerous Goods Regulations.

10.2.1 Clinical Blood Specimens

Blood specimens for safety and toxicity monitoring will be drawn at Baseline, Month 3, and Month 6/Post-intervention, and analyzed locally according to local institutional standard procedures. See Section 7.1 for the list of specific tests.

10.2.2 Research Blood Specimens

Blood specimens for endpoint analyses as well as optional blood specimens for future unspecified research will be drawn at Baseline, Month 3, and Month 6/Post-intervention. Blood specimens will be processed into serum, plasma, and buffy coat, and shipped to BAP overnight. See Section 10.1 for address. Detailed instructions for collecting, processing, labeling, and shipping the specimens can be found in the instructions provided in each blood specimen kit.

10.2.3 Tissue Specimen Collection and Submission for Central Pathology Review Histological confirmation of MAG, GIM, or both for eligibility will be determined based on local pathology review of the specimens collected during the baseline EGD procedure (See Appendix D). Representative specimens (blocks and/or slides) will be submitted for central review and confirmation. Digital images of all specimens will be created for the review and archiving processes. Discrepancies between local and central pathologists will be resolved on a case-bycase basis by teleconference or video conference between the local and central pathologists. Central pathology review will be performed at one time, when the study is completed, and is not part of the baseline evaluation.

Telepathology will be used to accomplish the goals of the study, and will be used as a pathology training platform. All specimens (histology slides) are de-identified. All study slides will be scanned and digitally archived for central review, discussion and training.

10.2.4 Research Tissue Specimens

Research tissue specimens will be collected at Baseline and Month 6/Post-intervention during the EGD procedures.

Biopsy specimens will be obtained during the EGD procedures. See Appendix D for locations from which the specimens will be collected. Specimens noted in Appendix D in green will be formalin-fixed and paraffin-embedded. At baseline, appropriate specimens will be sent to the local pathologist for determination of eligibility, i.e., presence of GIM and/or MAG. Remaining specimens will be used to determine Histology Gastric Score.

Specimens noted in Appendix D in red will be placed directly in screw-topped cryovials tubes with no preservative or buffer. The tubes will be snap-frozen by immersion immediately in dry ice or liquid nitrogen. To maintain the cold chain, specimens will be placed in a -70°C (or colder) freezer until shipment to BAP. See Section 10.3 for address. Shipping containers will be filled with 2-days' supply of dry ice, and all efforts necessary to prevent thaw during the shipping process will be implemented.

Biospecimen Summary

Specimen	Timepoint(s)	Processing	Shipping
Blood specimen for safety/toxicity monitoring. Specimen to be determined by local lab SOPS.	Baseline, Month 3, Month 6	Process according to local lab SOPs	Not applicable
H. pylori serology: Collect one 10mL no additive red-topped tube	Baseline	Process into serum, aliquot, freeze at -20°C or colder until shipment	Ship to BAP freezer (Address in Section 10.4) on dry ice for accessioning and storage. Storage at BAP will be at -70°C or colder; Ship in batches upon request by the University of Puerto Rico.
Mandatory: Stool testing for H. pylori antigen. Note: If a positive result is obtained, participant can be treated and then re-screened when a negative result is obtained.	Baseline	Collect and processing according to instructions in the stool antigen kit.	Not applicable
Risk genotype status: Collect one 10 mL (or two 4mL) EDTA purple- topped tube. Process using Qiagen Puregene solution in a 3:1 ratio	Baseline	Process EDTA purple topped tube into plasma and buffy coat, Freeze aliquots at -70°C or colder until shipment	Ship to BAP freezer (Address in Section 10.4) on dry ice for accessioning and storage; Storage at BAP will be at -70°C or colder; Ship in batches upon request by the University of Puerto Rico.
Optional research blood: Collect (1) one 10mL no additive red- topped tube and (2) one 10mL EDTA purple-topped tube,	Baseline, Month 6	 (1) Process red-topped tube into serum (2) Process EDTA purple topped tube into plasma and buffy coat Freeze aliquots at -70° C or colder until shipment 	Ship to BAP freezer (Address in Section 10.4) on dry ice for accessioning and storage. Storage at BAP will be at -70°C or colder.

Gastric biopsies noted in red in	Baseline,	Place specimens in individual	Ship to BAP freezer (Address in
Appendix D	Month 6	cryotubes, snap freeze	Section 10.4) on dry ice for
		immediately. Maintain at -	accessioning and storage; Storage at
		70° C or colder until	BAP will be at -70°C or colder; Ship in
		shipment	batches upon request by the
			University of Puerto Rico.
Gastric biopsies noted in green in	Baseline,	Formalin-fixed and paraffin-	At baseline, submit for central
Appendix D	Month 6	embedded.	pathology review (See Section 10.2.3).
			Baseline and Month 6 blocks or slides
			will be used to determine Gastric
			Histology Score.

10.3 Labeling and Shipping Instructions

The pre-addressed shipping labels will be provided with the specimen kits. Site teams are cautioned to make sure the correct specimen is sent to the correct location for analysis.

All specimens must be labeled completely and legibly with the study number, site number, participant ID, type of specimen, date and time of collection:

Example: MAY2015-05-01

MN026 CPN00023

EGD tissue biopsy mm/dd/2016, 14:30

All sections of the requisition form and specimen collection labels must be completed and legible.

All specimens (except biopsy specimens that are formalin-fixed and paraffin-embedded) should be sent over night (Monday through Friday) via FedEx® or World Courier on dry ice. Site staff will send an email with shipping tracking information to the Biospecimen Resource Manager so arrangements can be made to receive the specimens and place immediately in appropriate storage facilities. Exceptions for holidays will be communicated in advance to participating organizations. All samples must be shipped to the address provided on the specimen shippers and listed above (See Section 10.1).

[name], Biospecimens Resource Manager E-mail: [contact]; [contact]

Formalin-fixed, paraffin-embedded tissue (blocks or slides) from baseline and Month 6 EGD procedures will be sent to the University of Puerto Rico for central confirmation of baseline pathology review and for baseline and Month 6 measurement of Histology Gastric Score.

10.4 Tissue Banking

Biologic specimens collected during the conduct of each clinical trial that are not used during the course of the study will be considered deliverables under the contract and thus the property of the NCI.

At study completion, remaining frozen biologic specimens will be labeled (study number, participant ID number, specimen type, specimen number, date of collection) batched, and shipped (overnight, M-Th only) for storage (until request is received to transfer to DCP Biospecimens Repository) to:

Biospecimens Accessioning and Processing (BAP) Freezer [name]
[name]

At study completion, all remaining paraffin blocks and slides will be labeled (study number, participant ID number, specimen type, specimen number, date of collection) batched, and shipped (overnight, M-Th only) for storage (until request is received to transfer to DCP Biospecimens Repository) to:

CPN PC Office (Study MAY2015-05-01)
[name]
[name]

At study completion, NCI reserves the option to either retain or relinquish ownership of the unused biologic specimens. If NCI retains ownership of specimens, the Contractor shall collect, verify and transfer the requested biologic specimens from the site to a NCI-specified repository or laboratory at NCI's expense.

11. REPORTING ADVERSE EVENTS

DEFINITION: AE means any untoward medical occurrence associated with the use of a drug in humans, whether or not considered drug related. An AE can therefore be any unfavorable and unintended sign), symptom, or disease temporally associated with participation in a study, whether or not related to that participation. This includes all deaths that occur while a participant is on a study.

Please note that all abnormal clinical laboratory values that are determined to be of clinical significance based on a physician's assessment are to be reported as AEs. Those labs determined to be of no clinical significance or of unknown clinical significance (per the physician's assessment) should not be reported as AEs. Any lab value of unknown clinical significance should continue to be investigated/followed-up further for a final determination, if possible.

A list of AEs that have occurred or might occur can be found in §6.2 Reported Adverse Events and Potential Risks, as well as the Investigator Brochure or package insert.

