4.3 Registration/Randomization Inclusion Criteria

- 4.3.1 Histologically-confirmed chronic multifocal atrophic gastritis (MAG) and/or gastric intestinal metaplasia (GIM)
- 4.3.2 *Helicobacter pylori* negative, defined as negative stool antigen testing and negative histological examination.
- 4.3.3 ECOG performance status ≤1 (See Appendix A)
- 4.3.4 Participants must have normal organ and marrow function, defined as lab values (AST, ALT, Alkaline phosphatase, CBC [Platelets, Hemoglobin, WBC], BUN, Total bilirubin, Creatinine) within institutional limits of normal or judged to be not clinically significant by the investigator
- 4.3.5 Not pregnant or breast feeding. Note: The effects of Meriva® on the developing human fetus at the recommended therapeutic dose are unknown. For this reason, individuals of child-bearing potential and men must agree to use adequate contraception (hormonal or barrier method of birth control; abstinence) prior to study entry and for the duration of study participation. Should a woman become pregnant or suspect she is pregnant while participating in this study, she should inform her study physician immediately.

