Regarding utilization of doses higher than in the present study, a dose of 6000 mg curcuminoids/day was well tolerated with the reports of side effects being similar between the active treatment and placebo groups in a study of curcuminoids for the reduction of oral lichen planus. One systematic review of more than 60 completed studies of some form of curcumin, as well as a meta-analysis of randomized controlled trials for a variety of cancer and precancerous conditions, noted few reported adverse events even at doses of up to 8000 mg/day curcuminoids. Star Sharma, et al. reported on a clinical trial in advanced, refractory colorectal cancer involving 0.45 to 3.6 g daily curcumin in which there were 2 reports of diarrhea (Grade 2), one report of nausea (Grade 2), 4 reports of increases in alkaline phosphatase (Grades 1 and 2) and 4 reports of increased lactate dehydrogenase (Grade 1). Dose limiting toxicities were not observed. Dose-escalation studies indicate relative safety of curcumin at doses as high as 12 grams per day for 3 months.

Possible Side Effects of Meriva®*:

Rare, Some May Be Serious

In 100 people receiving Meriva, 3 or fewer may have:

- Loose stool (diarrhea)
- Stomach ache
- Feeling sick to your stomach (nausea)
- Muscle pain (myalgia)
- Joint pain (arthralgia)
- Skin discomfort

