11.1.3 Severity of AEs

11.1.3.1 Identify the AE using the active CTCAE (v4). The CTCAE provides descriptive terminology (MedDRA lowest level term) and a grading scale for each AE listed. A copy of the CTCAE can be found at

http://ctep.cancer.gov/protocolDevelopment/electronic applications/ctc.htm

AEs will be assessed according to the grade associated with the CTCAE term. AEs that do not have a corresponding CTCAE term will be assessed according to the general guidelines for grading used in the CTCAE v4 as stated below.

CTCAE v4 general severity guidelines:

Grade	Severity	Description
1	Mild	Mild; asymptomatic or mild symptoms; clinical or diagnostic observations only; intervention not indicated.
2	Moderate	Moderate; minimal, local or noninvasive intervention indicated; limiting age-appropriate instrumental activities of daily living (ADL)*.
3	Severe	Severe or medically significant but not immediately life- threatening; hospitalization or prolongation of hospitalization indicated; disabling; limiting self-care ADL**.
4	Life-threatening	Life-threatening consequences; urgent intervention indicated.
5	Fatal	Death related to AE.

ADL

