13.7 Evaluation of Toxicity (secondary endpoint)

All participants will be evaluable for adverse events (AEs) from the time of their first dose of Meriva® or placebo. To evaluate the AE profiles associated with each arm, the maximum grade for each type of adverse event will be recorded for each participant and frequency tables will be reviewed to determine the overall patterns. The number and severity of adverse events (overall and by intervention group) will be tabulated and summarized. Grade 3+ adverse events will be similarly described and summarized separately. As per NCI CTCAE, toxicities are defined as adverse events that are classified as either possibly, probably, or definitely related to the interventional agent. Overall toxicity incidence, as well as toxicity profiles will be explored and summarized within and between the 2 intervention arms. Frequency distributions, graphical techniques, and other descriptive measures will form the basis of these analyses. In addition, we will review all adverse event data that are graded as 3, 4, or 5 and classified as either "unrelated or unlikely to be related" to the study intervention in the event of an actual association developing.

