13.7.1 Adverse Event Stopping Rule

The trial will be monitored closely for occurrence of adverse events by the study team and by the Mayo Clinic Cancer Center Data Safety and Monitoring Board (DSMB) using the adverse event (AE) stopping rule specified below:

Adverse Event Stopping Rule: The stopping rule specified below is based on the knowledge available at study development. We note that the Adverse Event Stopping Rule may be adjusted in the event of either (1) the study re-opening to accrual after any temporary suspension or (2) at any time during the conduct of the trial and in consideration of newly acquired information regarding the adverse event profile of the treatment(s) under investigation. The study team in consultation with the Mayo DSMB may also choose to suspend accrual because of unexpected adverse event profiles that have not crossed the specified rule below.

Across all participants, accrual will be temporarily suspended to this study if at any time we observe events considered at least possibly related to study treatment (i.e., an adverse event with attribute specified as "possible", "probable", or "definite") that satisfy any of the following criteria for each arm separately:

If at any time 2 of the initial 10 treated participants or 20% of all participants (i.e. when accrual is greater than 10 participants) have experienced a grade 3 or higher adverse event.)

If at any time 1 participant experiences a Grade 4 or 5 AE that is at least possibly related to concomitant use of CYP sensitive substrate medications.

Each grade 5 event will be reviewed on a case by case basis in a real time fashion to determine whether study accrual should be suspended. We will also review all grade 4 adverse events regardless of attribution to monitor the emergence of any previously unrecognized treatment related adverse event.

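### Laboratory abnormalities of no or unknown clinical significance, at any grade, can be absent from every planned safety analysis; a by-arm laboratory table would close the gap

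*Combined protocol and SAP*

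**What the plan says.** Section 11 makes the reporting of a laboratory abnormality depend on a physician's judgement. A value judged clinically significant is an AE. Values "determined to be of no clinical significance or of unknown clinical significance" "should not be reported as AEs". No grade overrides this. The text separates unknown from none in one respect only: "Any lab value of unknown clinical significance should continue to be investigated/followed-up further for a final determination, if possible".

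Grading comes after that decision. Section 11.1.3 states that "AEs will be assessed according to the grade associated with the CTCAE term", and 11.1.2 lists severity grade and attribution among the data elements of an AE record. Section 11.1.5, on follow-up, again refers to laboratory abnormalities that the investigator considers significant.

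Safety is ranked first among the secondary endpoints, and 13.5 defines it as a comparison of AEs between arms. Section 13.7 adds: "The number and severity of adverse events (overall and by intervention group) will be tabulated and summarized". Section 13.7.1 suspends accrual, for each arm separately, when two of the first ten treated participants, or 20% once accrual exceeds ten, "have experienced a grade 3 or higher adverse event" that is at least possibly related to treatment.

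The schedule in 7.1 calls for AST, ALT, alkaline phosphatase, platelets, hemoglobin, WBC, BUN, total bilirubin and creatinine at baseline, Month 3 and Month 6. Criterion 4.3.4 admits participants whose values are "within institutional limits of normal or judged to be not clinically significant by the investigator".

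**The concern.** Nine analytes are measured twice on treatment for safety, yet the numbers themselves appear in no planned analysis. They reach the first-ranked secondary endpoint only if a local physician converts them into an AE. An unexplained change in a liver or renal test is likely to be labelled of unknown significance at first, and for reporting purposes that label has the same effect as a label of none.

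The plan does not otherwise rely on local judgement alone. Section 13.7 re-reads grade 3 to 5 AEs called unrelated or unlikely, in case an association emerges, and 13.7.1 reviews all grade 4 AEs whatever their attribution. Both reviews start from recorded AEs, so the significance call is made upstream of these safeguards. At stake is the trial's ability to show or exclude a laboratory effect, and the completeness of the count on which suspension depends.

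**Working it through.** The plan states no operating characteristics for the suspension rule and no expected rate of abnormal values, so there is no figure to reproduce. The check is mainly one of text.

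**1. Path of an abnormal value not judged significant**

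| Step | Section | What it requires | Does the value enter? |
|---|---|---|---|
| Reported as an AE | 11 | Judged clinically significant | No |
| Graded and attributed | 11.1.2 to 11.1.4 | An AE record | No |
| Safety endpoint | 13.5 | AEs | No |
| Toxicity tables | 13.7 | AEs | No |
| Review of unrelated or unlikely grade 3 to 5 events | 13.7 | AEs | No |
| Suspension rule and grade 4 review | 13.7.1 | AEs | No |
| Separate laboratory summary | 13 | None planned | No |

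The general description of grade 3 in 11.1.3 mentions medical significance. This does not rescue the value, because that scale is for AEs without a CTCAE term and applies only once something is an AE.

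**2. Timing.** A value of unknown significance becomes reportable if it is later judged significant. Section 11 sets no deadline for that decision, while 13.7.1 operates at any time. The value can therefore be counted late or never.

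**3. Baseline.** Because 4.3.4 admits abnormal values, AE reports alone cannot show change from baseline. A shift table can.

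**4. What a missed value does to the suspension count.** The two thresholds agree at the changeover (2/10 = 20%). For a missed value to matter, all of these must hold: it is grade 3 or higher; it would have been judged at least possibly related; its participant is not already counted, since the rule counts participants; and that arm is exactly one short.

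**5. Sensitivity of the rule to under-counting (illustration only).** Let p be the true proportion of participants with a qualifying event and m the share of those events not reported. Both are assumptions, because the documents give neither. With q = p(1 − m), the chance of at least two in the first ten is

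1 − (1 − q)^10 − 10q(1 − q)^9.

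For p = 20% and m = 25%, q = 0.15, giving 1 − 0.197 − 0.347 = 0.456.

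| p | m = 0 | m = 25% | m = 50% |
|---|---|---|---|
| 10% | 0.264 | 0.170 | 0.086 |
| 20% | 0.624 | 0.456 | 0.264 |
| 30% | 0.851 | 0.695 | 0.456 |

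Applying the full rule participant by participant over one arm of 25, the row for p = 20% becomes 0.772, 0.573 and 0.322. Here m is a share of all qualifying events, symptoms included. A laboratory gap alone could produce such an m only if laboratory values made up at least that share. The table shows that the rule is sensitive to under-counting; it does not size the laboratory gap.

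**The case against.** Section 11 is an explicit and internally consistent rule. A physician will usually call a grade 3 value significant, and unknown values are to be pursued. Participants and their care providers are blinded (6.9), so the call should not favour an arm. The toxicity analysis is descriptive with 25 per arm. Laboratory reports are source documents (12.3), so nothing is lost for good. Section 13.7.1 also lets the study team and the Data Safety Monitoring Board (DSMB) suspend accrual before the rule is crossed.

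Most of this stands and limits the point. It does not remove it: follow-up is conditional and undated, early suspension is still framed in terms of AE profiles, and blinding protects against bias but does not restore sensitivity.

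Four stronger readings are tempting, and the documents do not support them.

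- A reader might infer that the DSMB would never see such a value. Section 12.4 refers to a study-specific data and safety monitoring plan that was not supplied. One can say only that no route appears in the documents at hand.
- A reader might treat every planned on-treatment result as lost. Section 11 affects only abnormal values, and only those not judged significant.
- A reader might infer from 6.2 that a known laboratory signal is being filtered out. The cited colorectal cancer trial gives alkaline phosphatase rises as grades 1 and 2 without a split, and lactate dehydrogenase, its other signal, is not on this trial's panel. The same section notes no liver or kidney toxicity in an osteoarthritis study of Meriva.
- A reader might infer that any one missed grade 3 value decides suspension. The conditions in step 4 of the working show otherwise.

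**Conclusion.** The point holds as a gap in coverage. A laboratory shift, including a grade 3 value still of unknown significance, can be absent from the safety endpoint, the toxicity tables and the suspension count. The same is true of values judged to have no significance. The expected consequence is reduced sensitivity to a laboratory effect, not a comparison biased towards either arm. Its size cannot be given, because the documents contain no rate of abnormal, grade 3 or unresolved results.

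The conclusion assumes that the separate monitoring plan, and the data management plan cited in 12.1, add no laboratory analysis; neither was available. If either provides one, the remedy shrinks to a cross-reference in 13.7. The primary IL-1β analysis is unaffected. This is a worthwhile, inexpensive improvement to the first-ranked secondary endpoint.

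**What to change.** In 13.7, add a table by arm giving, for each of the nine protocol analytes, the maximum on-treatment grade on the numeric CTCAE v4 criteria (where the analyte has them) and the shift from baseline to worst value. Include every measured value, whatever the significance call. The laboratory normal ranges that 14.2.3 already requires supply the reference limits.

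Add a listing, for study team and DSMB review, of all grade 3 or higher laboratory values judged of no or unknown significance and therefore not reported as AEs. Covering both labels matters, since both keep a value out of the count.

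Ask the sponsor to reconcile Section 11 with 13.7.1 by stating how a grade 3 or higher value awaiting a significance decision relates to the suspension count. The suspension thresholds stay as they are.

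The cost is one table, one listing and a short clarification. No new blood draws or visits are needed. The protocol does not say that numeric results enter the study database, so some data entry may be required, and the table will carry a few rows of little information.
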